### 7.3.3. Proteinuria by Urinalysis (Dipstick)

The proteinuria by urinalysis (dipstick) toxicity grade (Grade 0 to Grade 3) at Weeks 12, 24, and 48 will be summarized by baseline proteinuria toxicity grade and treatment. In addition, the last on-treatment proteinuria toxicity grade will also be summarized by baseline proteinuria toxicity grade and overall and by Parts 1 and 2. On-treatment values include data collected after the last dose date up to the last dose date plus 1 day for subjects who permanently discontinued study drug.

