Subjects who complete the study through the Week 48 visit will be required to return to the clinic 30 days after the completion of study drugs for the 30-Day Follow-Up Visit.

Subjects who permanently discontinue study drug and refuse to continue study visits through Week 48 will be asked to return to the clinic after the completion of the ESDD visit for a 30-Day Follow-Up visit.

Those subjects who permanently discontinue study drug and continue in the study through at least one subsequent visit after the Early Study Drug Discontinuation Visit will not be required to complete the 30-Day Follow-Up Visit.

For the purpose of scheduling a 30-Day Follow-Up Visit, a ± 6 days window may be used. The following evaluations are to be completed at the 30-Day Follow-Up Visit:

- Review of AEs and changes in concomitant medications
- Symptom-directed physical examination as needed
- Vital signs (blood pressure, pulse, respiration rate, and temperature), including weight
- Urine collection for the following laboratory procedures:
 - Urinalysis and urine chemistry
- Blood sample collection for the following laboratory analyses:
 - Chemistry profile: alkaline phosphatase, AST, ALT, total bilirubin, direct and indirect bilirubin, total protein, albumin, bicarbonate, BUN, calcium, chloride, creatinine, glucose, potassium and sodium

- Hematology profile: CBC with differential and platelet count
- Plasma HIV-1 RNA
- CD4+ cell count

At the 30-Day Follow Up Visit, any evaluations showing abnormal results believed to be a reasonable possibility of a causal relationship with the study drug will be repeated weekly (or as often as deemed prudent by the Investigator) until the abnormality is resolved, returns to baseline, or is otherwise explained.

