7.5.4. Management of Potential Nephrotoxicity

Estimated glomerular filtration rate, according to the Cockcroft-Gault (eGFR_{CG}) formula for creatinine clearance, will be followed post-baseline during the study. All subjects with estimated eGFR_{CG} < 30 mL/min must have serum creatinine measured again within 3 calendar days of receipt of results. At the time of this repeat serum creatinine assessment, Cystatin C will also be measured and the eGFR by CKD-EPI (cystatin C) will be calculated and compared with the

baseline measurement. Any subjects who have an estimated $eGFR_{CG} < 30$ mL/min that also experience $> 20\%$ reduction in eGFR by CKD-EPI (cystatin C) from baseline or who have other clinical and/or laboratory evidence of acute renal failure will be discussed with the Medical Monitor and may discontinue from study drugs. For subjects with $eGFR_{CG} < 30$ mL/min who are not discontinued based on toxicity management procedures above and considered to have stable renal function per Principal Investigator and Medical Monitor, it is not mandatory to repeat eGFR assessments within 3 days.

CKD-EPI (cystatin C) formula adjusted for age and sex:

$$eGFR \text{ (mL/min/1.73m}^2\text{)} = 133 \times \min(\text{Scys}/0.8, 1)^{-0.499} \times \max(\text{Scys}/0.8, 1)^{-1.328} \times 0.996^{\text{Age}} \\ [\times 0.932 \text{ if female}]$$

where Scys is serum cystatin C (mg/L), $\min(\text{Scys}/0.8, 1)$ indicates the minimum of Scys/ κ or 1, and $\max(\text{Scys}/0.8, 1)$ indicates the maximum of Scys/ κ or 1. All subjects with a change from baseline serum creatinine of ≥ 0.4 mg/dL must have serum creatinine repeated, with a concurrent urinalysis and urine chemistry, within two weeks of receipt of results. If a subject has a confirmed change from baseline serum creatinine of ≥ 0.4 mg/dL, the Medical Monitor should be notified and a consultation with a nephrologist should be obtained.

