### 3.7.3. Selection of Data in the Event of Multiple Records in an Analysis Visit Window

Depending on the statistical analysis method, single values may be required for each analysis window. For example, change from baseline by visit usually requires a single value, whereas a time-to-event analysis would not require one value per analysis window. When a single value is needed, the following rule(s) will be used:

If multiple nonmissing numeric observations exist in a window, records will be chosen as follows:

- For baseline, the last available record on or prior to the date of the first dose of study drug will be selected. If there are multiple records with the same time or no time recorded on the same day, average (geometric mean for HIV-1 RNA and arithmetic mean for others) will be computed for that day.
- For postbaseline visits:

For key efficacy and safety data (ie, HIV-1 RNA level, CD4+ cell count, and CD4%), the latest record in the window will be selected.

For other numeric observations, the record closest to the nominal day for that visit will be selected. If there are 2 records equidistant from the nominal day, the latest will be selected.

If there is more than 1 record on the selected day, the average will be taken (geometric mean for HIV-1 RNA and arithmetic mean for others).

If multiple nonmissing categorical observations (eg, safety ECG results) exist in a window, records will be chosen as follows:

- For baseline, the last available record on or prior to the date of the first dose of the study drug will be selected. If there are multiple records with the same time or no time recorded on the same day, the value with the lowest severity will be selected (eg, normal will be selected over abnormal for safety ECG findings).
- For postbaseline visits, the most conservative value within the window will be selected (eg, abnormal will be selected over normal for safety ECG)

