## **7. SAFETY ANALYSES**

Safety data will be summarized for the subjects in the Safety Analysis Set. All safety data collected on or after the date of the first dose of study drug up to the last dose date of study drug plus 30 days for subjects who have permanently discontinued study drug, or all available data for subjects who are ongoing will be summarized overall and by Parts 1 and 2, unless specified otherwise. All safety data will be included in data listings.

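### On its natural reading, the Week 48 cell of the dipstick proteinuria shift table sets one baseline sample against the worst of up to two scheduled samples, one of them off drug

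*SAP*

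**What the plan says.** SAP 7.3.3 describes two dipstick summaries. In the first, the grade at each of three visits is tabulated against baseline: "toxicity grade (Grade 0 to Grade 3) at Weeks 12, 24, and 48 will be summarized by baseline proteinuria toxicity grade and treatment". The second tabulates the last on-treatment grade against baseline, with on-treatment data ending one day after last dose. That limit is attached to the second summary only.

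Neither summary has its own rule for several records in one window, so SAP 3.7.3 governs. Its rule for non-numeric results opens "If multiple nonmissing categorical observations (eg, safety ECG results) exist in a window". At baseline, "For baseline, the last available record on or prior to the date of the first dose of the study drug will be selected"; if that leaves tied records, "the value with the lowest severity will be selected". After baseline the direction reverses: "For postbaseline visits, the most conservative value within the window will be selected". For numeric safety results, 3.7.3 instead takes the record closest to the nominal day.

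SAP Table 3-2 sets the urinalysis windows: days 71-126 for Week 12, 127-210 for Week 24 and 295-378 for Week 48. SAP 7 keeps safety data "up to the last dose date of study drug plus 30 days for subjects who have permanently discontinued study drug", and SAP 7.2 repeats this for laboratory data.

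Protocol 6.4.2 includes urinalysis at the 30-Day Follow-up and adds: "For the purpose of scheduling a 30-Day Follow-Up Visit, a ± 6 days window may be used". Protocol 7.5.4 can generate further samples: subjects whose serum creatinine has changed by 0.4 mg/dL or more from baseline "must have serum creatinine repeated, with a concurrent urinalysis and urine chemistry, within two weeks of receipt of results".

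**The concern.** A shift table is read as a comparison of like with like. If one side is a single sample and the other is the worse of two, upward moves will outnumber downward moves even when nothing has changed. Here the second sample is a scheduled visit for every completer, and it is taken about a month after study drug has stopped.

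Two misreadings could follow. Proteinuria could appear to rise between Week 24 and Week 48 because the number of samples behind the cell rises from one to two. And a Week 48 worsening could come entirely from an off-drug sample. There is no control arm in which the same artefact would show. The quantitative proteinuria tables in SAP 7.3.4 rest on numeric values and so use the closest record; the two kinds of table could then disagree for the same subject and visit.

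**Working it through.** **1. The window.** The Table 3-2 limits are midpoints between nominal days. Weeks 36 and 48 are days 252 and 336, with midpoint 294, so Week 48 opens on day 295. It closes 42 days after nominal, at 336 + 42 = 378. Both limits match the SAP.

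**2. Scheduled urinalyses per window.** The scheduled days are 28, 56, 84, 168, 252 and 336, plus follow-up at about 336 + 30 = 366. Week 16 has no urinalysis. The count is one in each of the Week 4, 8, 12, 24 and 36 windows, and two in the Week 48 window (days 336 and 366).

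**3. Does the follow-up sample count?** Take Week 48 at day 336 ± 6 (the scheduling window in Protocol 6.3.1), last dose on that visit day, and follow-up at last dose + 30 ± 6.
- Inside the window: the follow-up day runs from 330 + 24 = 354 to 342 + 36 = 378. All 13 × 13 = 169 combinations fall within 295-378.
- Inside the data cut-off: the follow-up must come 24 to 30 days after last dose. That is 7 of 13 days, or 91 of 169 combinations (54%) if visits are spread evenly. A visit on its nominal day qualifies.

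**4. Size with no true change.** Inputs:
- p, the chance that any one sample is Grade 1 or higher. The documents do not give it; assumed 5%, 10% and 20%.
- ρ, the within-subject correlation between samples. Assumed 0 and 0.5.
- f = 7/13, the share of subjects with a second countable sample.
- N = 64, the reduced sample size in SAP 1.3, with everyone assumed to complete.

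Let P0(k) be the probability that k samples are all Grade 0. With ρ = 0, P0(k) = (1−p)^k. With ρ = 0.5 (beta-binomial), P0(1) = 1−p, P0(2) = (1−p)(2−p)/2 and P0(3) = (1−p)(2−p)(3−p)/6.

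- Upward = (1−f)[P0(1)−P0(2)] + f[P0(1)−P0(3)]
- Downward = (1−f)[P0(1)−P0(2)] + f[P0(2)−P0(3)]
- Net = f[P0(1)−P0(2)] = f·p(1−p)(1−ρ)
- Grade 1 or higher at Week 48 = p + net

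Worked case, p = 10% and ρ = 0: net = (7/13) × 0.10 × 0.90 = 0.0485, and 64 × 0.0485 = 3.1 subjects. With ρ = 0.5 this halves to 1.6.

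| p | ρ | Grade ≥1 at Week 48 | Upward | Downward | Net, of 64 |
|---|---|---|---|---|---|
| 5% | 0 | 7.6% | 7.2% | 4.6% | 1.6 |
| 5% | 0.5 | 6.3% | 3.2% | 1.9% | 0.8 |
| 10% | 0 | 14.8% | 13.4% | 8.5% | 3.1 |
| 10% | 0.5 | 12.4% | 6.0% | 3.6% | 1.6 |
| 20% | 0 | 28.6% | 22.9% | 14.3% | 5.5 |
| 20% | 0.5 | 24.3% | 10.6% | 6.3% | 2.8 |

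If every follow-up sample counted (f = 1), the net would be 1.5-3.0, 2.9-5.8 and 5.1-10.2 subjects.

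**5. With one sample per window.** Setting f = 0 makes upward and downward equal. At p = 10% that is 5.8 each way (ρ = 0) or 2.9 each way (ρ = 0.5), and the net is zero for every p and ρ.

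**The case against.** The SAP never says that a dipstick grade is categorical. The only example in 3.7.3 is the safety ECG, and item 22 of SAP Appendix 5 restates the worst-value rule for ECGs alone. If Grades 0 to 3 were programmed as numbers, the closest record would be chosen and the artefact would vanish. It would also vanish if the on-treatment limit was meant for the by-visit table. This stands as a limit on certainty. It does not remove the point: the ECG is given only as an example, the dipstick scale in Protocol Appendix 4 is ordinal (1+, 2-3+, 4+), and the numeric rule averages same-day records, which makes little sense for a grade.

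The same section also contains a safeguard. The last on-treatment shift table takes one value, ends one day after last dose and so excludes the follow-up sample; the laboratory listings show each sample by date. A careful reader could trace a Week 48 worsening to its source. This stands, and it lowers the stakes.

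Taking the worst value and keeping data for 30 days after last dose are ordinary safety conventions, and the error is toward over-reporting harm. That is a good reason to use them in a worst-ever table. It is a weaker one in a by-visit comparison with a single baseline record.

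A reader might infer that every visit in the table is biased. The documents do not support that: Weeks 12 and 24 hold one scheduled urinalysis each and gain extra records only from unscheduled repeats or samples around early discontinuation, whose frequency is not given. Nor does the lowest-severity rule generally pull baseline down; it settles only tied same-day records.

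**Conclusion.** The point holds for one cell of one table, on the natural reading of SAP 3.7.3. The Week 48 dipstick grade is the worst of up to two scheduled samples, and with no true change it drifts upward against baseline and against Weeks 12 and 24. The direction follows from the selection rule unless the two samples always agree.

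The size rests on assumed rates: a net excess of about 0.8-1.6, 1.6-3.1 or 2.8-5.5 of 64 subjects for per-sample rates of 5%, 10% or 20%, across correlations of 0.5 to 0. It also assumes that all 64 complete, that last dose falls on the Week 48 visit day and that follow-up visits are evenly spread. The model counts only moves between Grade 0 and Grade 1 or higher. Two samples from one person about a month apart are unlikely to be independent, so the lower end of each range deserves at least equal weight.

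It would go too far to say that the trial's renal safety conclusion is compromised. Proteinuria is not a protocol endpoint, the table is descriptive with no formal testing, and the last on-treatment table does not have this problem. This is a cheap clarification worth making.

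**What to change.** Add one sentence to SAP 7.3.3: for the Week 12, 24 and 48 shift table, use the on-treatment dipstick record (up to last dose + 1 day) closest to the nominal day. This matches the closest-record rule that already applies to UPCR and UACR in 7.3.4 and settles whether the grade is handled as categorical. The closest-record rule alone would usually pick the Week 48 sample over the follow-up; the on-treatment limit also stops a follow-up sample from standing in when the Week 48 sample is missing. State the start of the on-treatment period explicitly: 7.3.3 as worded begins it after the last dose date, while the UACR text in 7.3.4 begins after the first.

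Keep the worst post-baseline grade in the treatment-emergent laboratory table (SAP 7.2.2.2), where worst-ever is the aim.

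The cost is one sentence and a record-selection change in one table. A transient higher grade on a repeat or follow-up sample would leave the by-visit table, but it would remain in 7.2.2.2 if within 30 days of last dose, and in the listings. A completer with no on-treatment urinalysis in the Week 48 window would be missing from that cell.

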Laboratory analyses (CD4+ cell count, estimated glomerular filtration rate [eGFRCG], serum chemistry, hematology, urinalysis and urine chemistry, pregnancy testing [for females of childbearing potential]), and vital signs are performed at screening, baseline, Week 4, Week 8, Week 12, Week 24, Week 36, and Week 48/ESDD visit. Metabolic assessments are performed at baseline, Week 24, and Week 48.

12-Lead electrocardiogram (ECG) (performed supine) is collected at screening and Week 48/ESDD only.

Hepatitis B virus (HBV) and hepatitis C virus (HCV) serologies (ie, HBV virus surface antigen [HBsAg], hepatitis B core antibody [HBcAb], and hepatitis C virus [HCVAb] serologies [reflex HCV RNA is performed in subjects with positive HCVAb serology]) are performed at screening only. Height is collected at screening only.

For further details of assessments taken at each visit, see Schedule of Assessments, [Appendix 1](#).

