### **3. GENERAL CONSIDERATIONS FOR DATA ANALYSES**

Analysis results will be presented using descriptive statistics. For categorical variables, the number and percentage of subjects in each category will be presented; for continuous variables, the number of subjects (n), mean, standard deviation (SD) or standard error (SE), median, first quartile (Q1), third quartile (Q3), minimum, and maximum will be presented.

By-subject listings will be presented for all subjects in the All Enrolled Analysis Set unless otherwise specified, and sorted by subject identification (ID) number, visit date, and time (if applicable). Data collected on log forms, such as AEs, will be presented in chronological order within subject. The part (e.g. Part 1 or Part 2) under which subjects were enrolled will be included in the listings.

In general, age (in years) on the date of the first dose of study drug will be used for analyses and presentation in listings. If a subject was not dosed with study drug, the date of enrollment will be used instead of the first dose date of study drug. For screen failures, age as calculated on the date that informed consent was signed will be used.

In general, permanent discontinuation of study drug refers to premature discontinuation of study drug or completeness of study drug.

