#### 6.2.2.6. Analysis of CD4+ cell count

Analysis of CD4+ cell count will be based on on-treatment data (ie, data collected up to 1 day after the last dose date of study drug) using observed data (ie, missing will be excluded) for subjects in the FAS.

The change from baseline in CD4+ cell count at Weeks 12, 24, and 48 will be summarized overall and by Parts 1 and 2 using descriptive statistics. The change from baseline in CD4+ cell count will be similarly summarized at the visits other than Weeks 12, 24, and 48.

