### 7.3.4. Proteinuria by Quantitative Assessment

The baseline, postbaseline, changes from baseline, and percentage change from baseline in urine protein to creatinine ratio (UPCR) and urine albumin to creatinine ratio (UACR) will be summarized overall and by Parts 1 and 2 for each visit using descriptive statistics.

The number and percentage of subjects with UPCR  $\leq$  200 mg/g versus  $>$  200 mg/g will be summarized by baseline category at Weeks 12, 24, and 48, and based on the last on-treatment value (up to 1 day after the last dose date of study drug {[KDIGO Guideline Development Staff 2013](#)}).

The number and percentage of subjects with UACR  $<$  30 mg/g versus  $\geq$  30 mg/g will be summarized by baseline category at Weeks 12, 24, and 48, and the last on-treatment value (after first dose date up to 1 day after the last dose date of study drug {[KDIGO Guideline Development Staff 2013](#)}).

Median (Q1, Q3) percentage change from baseline in UPCR and UACR over time will be plotted.

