- c) For glucose grading, as specified in SAP Section 7.2.2.1, the treatment-emergent flag cannot be determined for nonfasting glucose (including glucose results without a known fasting status). As a result, these records will be excluded from the “Maximum Treatment-emergent Toxicity Grade” summary in the “Treatment-emergent Laboratory Abnormalities” or “Treatment-emergent Grade 3 or 4 Laboratory Abnormalities” summary tables. In addition, fasting glucose and nonfasting glucose will be listed as two separate laboratory tests in the “Laboratory Abnormalities” and “Grade 3 or 4 Laboratory Abnormalities” listings. Only a maximum postbaseline toxicity flag will be displayed and the treatment-emergent flag will not be displayed for nonfasting glucose as the treatment-emergent flag cannot be determined for nonfasting glucose.

25) “On-treatment” HIV-1 RNA data in the SAP refer to the data up to 1 day after the date of premature discontinuation of study drug (eg, last dose date).

26) Primary and Efficacy analyses:

- a) Listing for snapshot algorithm outcome:

In addition to flagging the values of HIV-1 RNA  $< 50$  or  $\geq 50$  for snapshot algorithm virologic outcomes, flag the last available HIV-1 RNA value for the following categories:

- i) HIV-1 RNA  $> 50$  copies/mL - Discontinued Study Drug Due to AE or Death and Last Available HIV-1 RNA  $> 50$  copies/mL
- ii) HIV-1 RNA  $> 50$  copies/mL - Discontinued Study Drug Due to Other reason\* and Last Available HIV-1 RNA  $> 50$  copies/mL
- iii) No virologic Data Discontinued Study Drug Due to AE or Death and Last Available HIV-1 RNA  $< 50$  copies/mL

iv) No virologic Data Discontinued Study Drug Due to Other reason\* and Last Available HIV-1 RNA < 50 copies/mL

Note: \* Other reasons include subjects who discontinued study drug due to investigator's discretion, subject decision, lost to follow-up, noncompliance with study drug, protocol violation, pregnancy, and study terminated by sponsor.

- b) For patients discontinued study drugs, if the last HIV-1 RNA (< 50 copies/mL) was on the same day as the start date of a new non-study ARV, the subjects was not a failure for the Snapshot outcome.
- c) For a subject who completed the study drug with Week 48 HIV-1 RNA missing, snapshot outcome for such subject would be "Missing data during the windows but on study drug".

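### SAP 7.3.3 starts the on-treatment window for dipstick proteinuria at the last dose rather than the first, contradicting the UACR definition in 7.3.4

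*SAP*

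**What the plan says.** SAP 7.3.3 plans two dipstick outputs. One tabulates toxicity grade at Weeks 12, 24 and 48 by baseline grade. The other tabulates the last on-treatment grade by baseline grade, overall and by Part. For the second it gives a definition, applied to subjects who have permanently stopped study drug: "On-treatment values include data collected after the last dose date up to the last dose date plus 1 day".

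That group is wide. SAP Section 3 says that, in general, "permanent discontinuation of study drug refers to premature discontinuation of study drug or completeness of study drug". The final analysis follows completion of the study by all subjects (SAP 2.3), so by then the rule reaches completers as well as early discontinuers.

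The next section, SAP 7.3.4, uses the same idea for the quantitative urine ratios. For UACR the window runs "after first dose date up to 1 day after the last dose date of study drug". For UPCR the summary is "based on the last on-treatment value (up to 1 day after the last dose date of study drug".

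**The concern.** A window meant to capture values on treatment should open at the start of treatment. This one opens after treatment has ended and closes a day later. The sentence is also the only stated selection rule for the last on-treatment dipstick table. The one general programming note on the term, item 25 in SAP Appendix 5, is limited to HIV-1 RNA, so a programmer has nothing else to fall back on.

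At stake is whether that table reflects each subject's last dipstick on drug or a subset fixed by which day the final sample happened to be drawn. Two programmers could reasonably build it in two different ways.

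**Working it through.** The plan gives no figure to reproduce. The check compares the definitions and then counts which scheduled samples fall in each window.

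**Definitions side by side**

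| Measure | SAP place | Start | End |
|---|---|---|---|
| Dipstick proteinuria | 7.3.3 | after last dose | last dose + 1 day |
| UACR | 7.3.4 | after first dose | last dose + 1 day |
| UPCR | 7.3.4 | not stated | last dose + 1 day |
| CD4+ count | 6.2.2.6 | not stated | last dose + 1 day |
| CD4% | 6.2.2.7 | not stated | last dose + 1 day |
| Snapshot HIV-1 RNA | 6.2.2.3 | not stated | last dose + 1 day |
| HIV-1 RNA, item 25 | Appendix 5 | not stated | discontinuation + 1 day |

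The wording behind the rows: UACR, "the last on-treatment value (after first dose date up to 1 day after the last dose date of study drug"; CD4+, "on-treatment data (ie, data collected up to 1 day after the last dose date of study drug"; item 25, "HIV-1 RNA data in the SAP refer to the data up to 1 day after the date of premature discontinuation of study drug". All seven share the same kind of upper limit. Only 7.3.3 puts its lower limit at the last dose. Its phrasing runs close to the UACR sentence, with *last* where that has *first*.

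**Window length.** Let L be the study day of the last dose.

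- 7.3.3 read literally: L < day ≤ L + 1, which is one day. With L = 336, Day 337 only.
- UACR rule: 1 < day ≤ L + 1. With L = 336, Days 2 to 337, which is 337 − 2 + 1 = 336 days.

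**Which scheduled samples qualify.** SAP 1.2 sets the schedule in a sentence that covers urinalysis along with other assessments: "vital signs are performed at screening, baseline, Week 4, Week 8, Week 12, Week 24, Week 36, and Week 48/ESDD visit". That gives six post-baseline treatment visits (Weeks 4, 8, 12, 24, 36 and 48) plus the early study drug discontinuation (ESDD) visit. Under the literal rule:

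- Weeks 4 to 36: all excluded for a completer.
- Week 48: drug stops after this visit (protocol synopsis) and none is dispensed at it (protocol Appendix 2). With a sample on Day 336, a last dose on Day 336 fails (337 is required) and a last dose on Day 335 qualifies (335 + 1 = 336).
- ESDD: due within 72 hours of the last dose (protocol Appendix 2). Only a sample dated exactly L + 1 qualifies.
- 30-day follow-up: outside both windows.

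**Number of subjects left.** Let f be the share with a dipstick sample dated L + 1. The documents do not give f, so it is an assumption. Taking the revised size of 64 (SAP 1.3), with all dosed and sampled, the table holds 64 × f subjects:

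| f | Subjects |
|---|---|
| 0% | 0 |
| 10% | 6.4, about 6 |
| 25% | 16 |
| 50% | 32 |
| 100% | 64 |

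**The case against.** The best defence rests on the word *include*. The sentence can be read as adding one day after the last dose to data already counted as on drug. That reading gives the same upper limit as the other definitions and is probably close to what was meant. It stands as a possible reading, but it does not rescue the text: the sentence would then state no start point, while the UACR rule does.

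A reader might infer that the table would be nearly empty. The documents do not support that. The one-day window sits next to the visits that supply the final sample, and on a once-daily drug a last dose on the day before the visit puts the sample inside it. The split between that case and a last dose on the visit day is not given.

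A reader might also infer that the table would hold off-drug values. That is too strong, because the SAP itself counts the day after the last dose as on treatment for viral load, CD4+ count, CD4%, UPCR and UACR.

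It is also fair to say that little depends on this table. It is descriptive, and SAP 7.2 plans no formal laboratory testing. Dipstick proteinuria is a graded test (protocol Appendix 4), so its treatment-emergent abnormalities are captured by worst grade up to last dose plus 30 days (SAP 7.2.2.1 and 7.2.2.2; Appendix 5, item 24a). Urinalysis results are listed by subject (SAP 7.2). All of this limits the consequence; none of it makes the sentence right.

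**Conclusion.** The start of the dipstick window in SAP 7.3.3 is wrong as written. It contradicts the UACR definition in the next section and is out of line with every other on-treatment definition in the SAP. The likeliest explanation is a drafting slip rather than a chosen window.

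Taken literally, it discards all samples up to and including the last dose date from the last on-treatment dipstick table. The number of subjects left is indeterminate, from 0 to 64, assuming the revised sample size is met and all subjects are dosed and sampled. Taken additively, it leaves the start undefined.

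The point is minor. The fixed-visit dipstick tables at Weeks 12, 24 and 48 are not tied to this sentence, and UPCR, UACR, the graded laboratory summaries and efficacy do not use it.

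**What to change.** In SAP 7.3.3, define on-treatment dipstick values as those collected *after the first dose date up to the last dose date plus 1 day*, matching the UACR text in 7.3.4. This changes one word. It needs no new data and no change to design or to other outputs. The program for this one table should be checked against the corrected sentence.
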